5.0 DATA COLLECTION AND RETENTION

The study endpoints data will be collected from each participant's study questionnaires. The data will be collected electronically via the patient's own device and uploaded to an electronic data capture system. The data will be used to measure whether the Nu-V3 device provides participants with a reduction in participants' chronic pain, anxiety, depression, and/or sleeplessness.

The data analysis will include baseline data for each participant's questionnaire prior to beginning treatment with the Nu-V3 device. Longitudinal data will consist of participant's weekly questionnaires measuring chronic pain, anxiety, depression, and sleeplessness during the treatment phase. The final data collection will be completed by participants at the end of the treatment with the Nu-V3 device and will measure chronic pain, anxiety, depression, and sleeplessness.

The Principal Investigator at each site will be responsible for recording, collecting, and storing the research participant's study data. The written records will be stored in a secure location. Only the Principal Investigator or designated study staff will have access to the study records and all electronic files will be password protected. The Principal Investigator will also maintain adequate records for the study including:

- all correspondence with the IRB and Sponsor
- other pertinent data related to the study

All records are to be retained by the Principal Investigator for a period of three (3) years following the closure of the study. Following study closure, the Principal Investigator shall inform Nu-Life of the location of study records and storage changes (i.e., the Principal Investigator leaves the institution where the study was conducted). In such cases, the study records may be transferred to another institution, investigator, or to Nu-Life upon written agreement between the Principal Investigator and Nu-Life.

6.0 DATA DISCLOSURE AND SUBJECT CONFIDENTIALITY

Medical record confidentiality and data protection will be maintained at every visit. Subject medical information obtained because of this study is considered confidential and disclosure to third parties, other than those noted below, is prohibited. Data generated during this study is to be available for inspection on request by the FDA or other government regulatory agency auditors, the Sponsor's authorized representatives, and the IRB.

7.0 ADVERSE EVENT(S)

Subjects will be evaluated for safety if they have received any study treatment. Adverse event assessments will be continuous during the 24-week trial (see section 4.1). During

treatment visits, toxicity assessments should be done in person. Once subjects reach symptom stabilization and are not actively receiving device therapy, follow-up either in person or documented via telephone call, is acceptable. Adverse events and will be graded according to the NIH-CTCAE version 5.0.

Potential unanticipated problems require prompt reporting to the central IRB and study sponsor. These problems potentially place subjects or others at greater risk of physical or psychological harm than was previously recognized, and warrant consideration of substantive changes in the protocol or informed consent process or other action to protect the safety, welfare, or rights of participants. The central IRB must be notified within 5 calendar days of the event and the study sponsor within 24 hours. The completed IRB Unanticipated Problem Form (Appendix 7) must be received by the central IRB within 10 calendar days of the event to avoid a major deviation.

Unanticipated problems are defined as those problems which alter the risks to subjects or others. This includes any study suspensions or holds. This form will be used to report any problem that is unforeseen or involves risk. One form will be used per event or problem.

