Subjects randomized to the observation control arm of the study will undergo the following regimen:

- At the baseline visit, patients will be asked to complete study questionnaires (Appendix 11) regarding all the following symptoms: chronic pain, anxiety, depression, and/or sleeplessness, as well as their quality of life, active medications, medical history, and demographical information. The subject's primary symptom of concern will also be notated at baseline.
- At each subsequent visit, patients will be asked to complete study questionnaires regarding all the following symptoms: chronic pain, anxiety, depression, and/or sleeplessness, as well as their activity level and quality of life.
- Patients should not change their existing forms of treatment or medications without discussion with the study investigator.
- At completion of 12 weeks of standard of care treatment post study enrollment, observation (control arm) subjects will be offered a crossover into the treatment arm of the study for an additional 24 weeks.

Sample size

For this Phase II study, a total of 100-200 subjects will be randomized 1:1 to either the Nu-V3 treatment arm or to the observation treatment arm (SOC, control).

Recruitment

Participants are enrolled into relevant symptom cohorts based on their chronic pain, anxiety, depression, and/or sleeplessness symptom presentation at baseline and treated with the Nu-V3 device for 24 weeks.

Analyses

Interim analysis of reported data will be based on baseline symptom cohort and conducted at 6, 12, 18, and 24 weeks during this time. The participant will be evaluated after the initial 12-week treatment period to assess for further therapeutic need. Upon having three consecutive weeks of mean symptom reduction of $\geq 70\%$ via patient reported numerical scales, the participant will continue as described in the study assessments table, but without device therapy. Then if the participant's primary

symptom score increases at any time by $\geq 20\%$, they may again continue device therapy until week 24, as depicted in section 4.1.

Study subjects randomized to the observation arm will be offered the opportunity to cross-over to the Nu-V3 study treatment arm upon completion of the initial 12-week observation study period.

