Nu-V3 Treatment Arm Evaluation*	Week 13	Week 14	Week 15	Week 16	Week 17	Week 18	Week 19	Week 20	Week 21	Week 22	Week 23	Week 24
Medications Form ¹				x				x				x
In office assessment	x	x		x	x		x	x		x	x	x
New Device Placed ²	x			x			x			x		
Pad Replaced ²		x			x			x			x	
Treatment Forms ¹	x	x		x	x		x	x		x	x	
No Device			x			x			x			x
HRV Assessment (optional) ³	x	x		x	x		x	x		x	x	
ePRO Questionnaires ⁴	x	x	x	x	x	x	x	x	x	x	x	x
Patients' Global Impression of Change ePRO form (PGIC) ⁴	x	x	x	x	x	x	x	x	x	x	x	x
Providers' Global Impression of Change ePRO form (PGIC) ¹		x			x			x		x	x	
Optional Patient Media Testimony ⁵	x	x		x				x				x

1. Providers' PGIC form, Medications and Treatment forms to be completed by site via online module.
2. Upon having three consecutive weeks of mean symptom reduction of ≥70% via patient reported numerical scales, the participant will continue as described in the study assessments table, but without device therapy. Then if the participant's primary symptom score increases at any time by ≥20%, they may again continue device therapy until week 24.
3. (Optional) HRV assessment before the first treatment and again 15-20 minutes following the first treatment. HRV assessment will also be conducted prior to each weekly treatment. This assessment is applicable to participating sites per the clinical trial agreement. Contact the clinical trial manager for information.
4. ePRO questionnaires completed on patient's mobile device: DQ-9 (baseline), PTB-7, PEG, GAD-7, PHQ-9, PROMIS 4a, PGIC
5. If patient consents to media testimony, site will collect via study collection process.

Nu-Life Solutions Miniaturized Wearable Medical Technology - NuJ ³	Control Study Assessments Table											NuJ ³
	*Evaluations are completed weekly, every 7 days ±3 days											
Control Arm Evaluation*	Week 1	Week 2	Week 3	Week 4	Week 5	Week 6	Week 7	Week 8	Week 9	Week 10	Week 11	Week 12
Informed Consent	x											
Inclusion and Exclusion ¹	x											
Patient Registration ¹	x											
Medications Form ¹	x			x				x				x
Patient Onboarding and Orientation ²	x											
In office assessment	x			x				x				x
No Device	x	x	x	x	x	x	x	x	x	x	x	x
ePRO Questionnaires ³	x			x				x				x
Patients' Global Impression of Change ePRO form (PGIC) ³				x				x				x

1. Inclusion/Exclusion, Registration, Medications, Treatment, and Providers' PGIC forms to be completed by site via online module.

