8.0 STUDY ENDPOINT and DATA ANALYSIS

8.1 Primary Endpoints: Primary endpoints consisted of the following:

Safety: At screening/baseline, a medical history will be obtained to capture relevant underlying conditions. The screening/baseline examinations will include BP, and HR. Baseline signs and symptoms are those that are assessed within 14 days prior to week 1 treatment.

Concomitant medications will be collected from within 14 days prior to enrollment through the study treatment period and maintenance period (see Study Assessments Table section 4.1).

The primary safety endpoint is the occurrence of reported unanticipated problems involving risk to subjects or others (“UPIRTSOs”). These UPIRTSOs are defined as those problems which alter the risks to subjects or others. This includes any study suspensions or holds. The primary safety endpoint analyses will be based on a risk-benefit conclusion.

Effectiveness: There are four instruments measuring participant’s symptoms of chronic pain, anxiety, depression, and sleeplessness. The primary effectiveness endpoint is a statistically significant reduction in one or more of measures of: chronic pain, anxiety, depression, or sleeplessness between baseline and 12 or 24 weeks after initiating treatment.

The null hypothesis to disprove is that there is no statistically significant reduction from baseline to 12 or 24 weeks in mean chronic pain, anxiety,

depression, or sleeplessness symptom severity scores using the Nu-V3 device compared with the usual care cohort.

The instruments used in this study are:

Chronic Pain – Pain intensity (P), interference with enjoyment of life (E), and interference with general activity (G) (PEG Scale),

The PEG is a three-item instrument that measures pain intensity (one item) and pain interference (two items). Each item is valued from 0 (no pain/interference) to 10 (as bad as you can imagine). The instrument score is calculated as the average of the three item values.

Anxiety - Generalized Anxiety Disorder 7-item (GAD-7)

The GAD-7 is a seven-item instrument that measures respondents' symptoms of anxiety. Each item is scored on a four-point Likert scale, and values range from 0 ("Not at all") to 3 ("Nearly every day".) Items are summed to determine the instrument's score. Values of 10 or higher have been associated with moderate anxiety, while values of 15 or higher have been associated with severe anxiety.

Depression - Patient Health Questionnaire (PHQ-9)

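### Section 7.0 ties safety evaluation to an undefined study treatment, and no adverse-event assessment is set out for controls, so a concurrent adverse-event comparison over weeks 1-12 is not assured

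*Protocol*

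**What the plan says.** Section 7.0 opens with the rule on who is assessed: "Subjects will be evaluated for safety if they have received any study treatment". The next sentence sets the period without naming an arm: "Adverse event assessments will be continuous during the 24-week trial (see section 4.1". The tables in section 4.1 contain no adverse-event row for either arm.

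Section 4.0 gives the allocation: "a total of 100-200 subjects will be randomized 1:1 to either the Nu-V3 treatment arm or to the observation treatment arm (SOC, control". Controls have 12 weeks of usual care and may then "cross-over to the Nu-V3 study treatment arm upon completion of the initial 12-week observation study period". In section 4.1, the table headed "Control Study Assessments Table" marks every control week as without a device and has in-office assessments at weeks 1, 4, 8 and 12. The device arm is seen in the office every week from 1 to 12.

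Section 8.1 defines the primary safety endpoint as the occurrence of reported unanticipated problems that alter risk to subjects or others (UPIRTSOs). It adds: "The primary safety endpoint analyses will be based on a risk-benefit conclusion". The effectiveness hypothesis in the same section is set against the usual care cohort.

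**The concern.** A safety set limited to treated subjects does no harm when every arm receives a study product. Here one arm receives none during the only randomised period, so the same rule can remove that arm from adverse-event assessment altogether.

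Patients with chronic pain, anxiety, depression or poor sleep can be expected to report health complaints whether or not they wear a device. Without the same inquiry in controls, a device-arm adverse-event rate cannot be compared with a background rate from the same trial. Benefit would be judged against a randomised comparator, while the adverse-event part of the risk judgement would have none. The rule governs data collection, so the loss cannot be repaired at the analysis stage.

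**Working it through.** The protocol states no safety figure, so there is none to reproduce. The check is mainly a reading of sections 4.0, 4.1, 7.0 and 8.1 and the safety forms.

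**Step 1. What the term means.** The protocol does not define *study treatment*. Three points favour the device:
- Section 4.0 has controls "cross-over to the Nu-V3 study treatment arm upon completion of the initial 12-week observation study period", which attaches the term to the Nu-V3 arm.
- If usual care counted, every randomised subject would qualify and the condition in section 7.0 would do no work.
- The rest of that paragraph in section 7.0 speaks of treatment visits and of subjects who are off device therapy. Its 24-week span is the device arm's duration; controls have 12 weeks and then an optional 24 weeks on the device.

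One point favours a broader meaning: section 4.0 also calls the control an observation treatment arm and describes its care as treatment.

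**Step 2. Who is assessed under each meaning.** A total of 100-200 at 1:1 gives 50-100 per arm.
- Device meaning: 0 of the 50-100 controls are in the safety evaluation in weeks 1-12. They enter only after crossover, when they are no longer a comparator.
- Broad meaning: all 100-200 are included, but controls have four in-office assessments in weeks 1-12 against twelve in the device arm, so ascertainment is unequal.

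**Step 3. The arm regimens in section 4.0.** The device sessions include an evaluation for device effects. The control regimen lists baseline data, questionnaires, advice about changing treatment, and the crossover offer. It lists no safety evaluation.

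**Step 4. What control data would buy (illustration).** The protocol gives no adverse-event rate. Assume a common rate p of 10% to 30% over 12 weeks, equal ascertainment and no dropout. The expected number of device subjects with a background event is n × p: 5-15 of 50, or 10-30 of 100.

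The 95% half-width for the risk difference is 1.96 × √(2p(1−p)/n):

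| p | n per arm | calculation | half-width |
|---|---|---|---|
| 0.10 | 50 | 1.96 × √(0.18/50) | 11.8 points |
| 0.30 | 50 | 1.96 × √(0.42/50) | 18.0 points |
| 0.10 | 100 | 1.96 × √(0.18/100) | 8.3 points |
| 0.30 | 100 | 1.96 × √(0.42/100) | 12.7 points |

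From a 10% control rate, 80% power at two-sided 0.05 would need a device rate of about 33% at 50 per arm or 25% at 100 per arm. The comparison would therefore show only large differences. Without control data it cannot be made at all.

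**The case against.** The case on the other side has five parts.

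- **Endpoint.** A reader might infer that the treated-only rule leaves the primary safety endpoint without a comparator. The protocol does not support that. The endpoint is reported UPIRTSOs, and section 7.0 has the reporting form used for any unforeseen or risk-related problem, affecting subjects or others, with no limit by arm. Section 8.1 states no between-arm safety comparison, and tabulation by arm is commonly left to an analysis plan. This part stands.
- **No control data at all.** A reader might also infer that controls certainly supply no adverse-event data. That is too strong. The term is undefined, the control is also called a treatment arm, the continuous-assessment sentence names no arm, and the Appendix 4 form is not arm-specific. This stands as a limit on certainty. It does not remove the need for a change: if the intention was to assess controls, section 7.0 does not say so.
- **The missing row.** The absence of an adverse-event row from the control table might be read as singling controls out. The device-arm tables lack one too, so the absence proves little alone. The difference lies in the regimens in section 4.0.
- **Other means of separating events.** Appendix 4 grades attribution on five levels, and Appendix 3 records alternative causes and whether the event stopped or recurred when the device was stopped or restarted. Controls also complete the four symptom scales at weeks 1, 4, 8 and 12, so worsening of those symptoms does have a comparator. These points stand, so it would be wrong to say that device events cannot be told from background at all. Attribution in an open-label trial is still no substitute for a concurrent rate.
- **Unequal contact.** Asking controls about monthly and device subjects weekly would tend to under-count control events and bias the difference against the device. This stands, and the fix must deal with it.

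**Conclusion.** The point holds as a gap in a stated collection rule. Followed on its most natural reading, section 7.0 leaves controls out of adverse-event assessment in the only randomised 12 weeks, and neither the control regimen nor the control table supplies it by another route. What is affected is the adverse-event information behind the risk-benefit judgement; the UPIRTSO count is not removed by this sentence.

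The conclusion rests on reading *study treatment* as the device, which is likely but not stated. The half-widths in the working rest on assumed event rates, equal ascertainment and no dropout. They show that the comparison would be imprecise, so this is a cheap improvement to the safety evidence and not a flaw that undermines the trial.

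**What to change.** 1. Replace the opening sentence of section 7.0 with: *All randomised subjects are evaluated for adverse events from enrolment.*
2. Add an adverse-event row to the section 4.1 tables for both arms.
3. Complete the Appendix 4 form for controls at their existing week 4, 8 and 12 visits.
4. At those three weeks, ask both arms the same question about the interval since the previous shared visit. Base the between-arm comparison on those answers, record onset dates, and report weeks 1-12 by randomised arm.
5. State that unequal contact in an open-label trial may still under-count control events. Onset dates help to examine this but do not recover events that were never reported.

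The cost is a sentence, a table row and a short form at visits that controls already attend, plus the same shared-visit question in the device arm. No new visits are needed. Fully matched ascertainment would need more control contacts, which is why the caveat in item 5 has to remain.

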8.0 STUDY ENDPOINT and DATA ANALYSIS

8.1 Primary Endpoints: Primary endpoints consisted of the following:

Safety: At screening/baseline, a medical history will be obtained to capture relevant underlying conditions. The screening/baseline examinations will include BP, and HR. Baseline signs and symptoms are those that are assessed within 14 days prior to week 1 treatment.

Concomitant medications will be collected from within 14 days prior to enrollment through the study treatment period and maintenance period (see Study Assessments Table section 4.1).

The primary safety endpoint is the occurrence of reported unanticipated problems involving risk to subjects or others (“UPIRTSOs”). These UPIRTSOs are defined as those problems which alter the risks to subjects or others. This includes any study suspensions or holds. The primary safety endpoint analyses will be based on a risk-benefit conclusion.

Effectiveness: There are four instruments measuring participant’s symptoms of chronic pain, anxiety, depression, and sleeplessness. The primary effectiveness endpoint is a statistically significant reduction in one or more of measures of: chronic pain, anxiety, depression, or sleeplessness between baseline and 12 or 24 weeks after initiating treatment.

The null hypothesis to disprove is that there is no statistically significant reduction from baseline to 12 or 24 weeks in mean chronic pain, anxiety,

depression, or sleeplessness symptom severity scores using the Nu-V3 device compared with the usual care cohort.

The instruments used in this study are:

Chronic Pain – Pain intensity (P), interference with enjoyment of life (E), and interference with general activity (G) (PEG Scale),

The PEG is a three-item instrument that measures pain intensity (one item) and pain interference (two items). Each item is valued from 0 (no pain/interference) to 10 (as bad as you can imagine). The instrument score is calculated as the average of the three item values.

Anxiety - Generalized Anxiety Disorder 7-item (GAD-7)

The GAD-7 is a seven-item instrument that measures respondents' symptoms of anxiety. Each item is scored on a four-point Likert scale, and values range from 0 ("Not at all") to 3 ("Nearly every day".) Items are summed to determine the instrument's score. Values of 10 or higher have been associated with moderate anxiety, while values of 15 or higher have been associated with severe anxiety.

Depression - Patient Health Questionnaire (PHQ-9)

The PHQ-9 is a nine-item instrument that measures depression-related symptoms and functional impairment. Each item is scored on a four-point Likert scale and values range from 0 ("Not bothered at all") to 3 ("Bothered nearly every day.") The items' values are summed to determine the instrument's score. PHQ-9 values of 10 and 15 represent moderate and moderately severe depression respectively.

Sleeplessness - PROMIS short form 4a

This eight item instrument measures sleep disturbance and sleep-related impairment.

8.2 Secondary Endpoints: Secondary endpoints consisted of the following:

Effectiveness: There are two secondary effectiveness endpoints:

1. In the Nu-V3 device treatment arm, the study will report the mean time from treatment initiation to reduction of symptoms of at least 30% in any of the four domains of symptom measurement.
2. In both the Nu-V3 device treatment arm and the observation arm, the study will report the mean percentage change in symptoms severity from initiation to 12 and 24 weeks for each instrument.

Additional secondary endpoints of this study are:

- Mean improvement in quality of life measured with Patient's Global Impression of Change (PGIC) between the treatment and usual care arm, and

- Mean improvement in activities of daily living via Perceived Treatment Benefit Form (PTB-6) between the treatment and usual care arm.

8.3 Sub-Analyses: Sub-Analyses consist of the following:

The study has several sub-analyses. They include:

- The mean number of weeks that chronic pain, anxiety, depression, and sleeplessness response are achieved and sustained, without utilization of another device or change in other treatments, during the full 24-week intervention in the Nu-V3 device treatment arm.
- The mean number of weeks to initial benefit from Nu-V3 device use in the Nu-V3 device treatment arm. Benefit is defined as a reduction of at least 30% of symptoms in at least one of chronic pain, anxiety, depression, or sleeplessness.
- **The device's comfort-of-use, and patient's perceived treatment benefit** in the Nu-V3 device treatment arm.

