Appendix 4: Adverse Event Form

Subject ID _____ Date (dd/mmm/yyyy): ____/____/____

Adverse Events Form

1. Has the participant experienced any adverse events?

- No (end of form)
 Yes (update log below)

2. Adverse Event Log (CTCAE 5.0)

Grade 1=Mild Grade 2=Moderate Grade 3=Severe Grade 4=Life-threatening Grade 5=Death
 Attribution Grading: A=unrelated B=unlikely C=possibly D=probably E=definitely

Event Name	SAE?	Grade	Attribution	Start Date (dd/mmm/yyyy)	End Date (dd/mmm/yyyy)	Treatment held or withdrawn?
	y/n		A B C D E			
	y/n		A B C D E			
	y/n		A B C D E			
	y/n		A B C D E			
	y/n		A B C D E			
	y/n		A B C D E			
	y/n		A B C D E			
	y/n		A B C D E			
	y/n		A B C D E			
	y/n		A B C D E			
	y/n		A B C D E			
	y/n		A B C D E			
	y/n		A B C D E			
	y/n		A B C D E			
	y/n		A B C D E			
	y/n		A B C D E			
	y/n		A B C D E			
	y/n		A B C D E			
	y/n		A B C D E			
	y/n		A B C D E			

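### The primary safety endpoint rests solely on reported unanticipated problems, so device-related adverse events within already recognized risk need not enter it, although Appendix 4 collects them

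*Protocol*

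**What the plan says.** Section 8.1 names one primary safety endpoint: "The primary safety endpoint is the occurrence of reported unanticipated problems involving risk to subjects or others". The definition follows: "These UPIRTSOs are defined as those problems which alter the risks to subjects or others". Two further sentences complete it: "This includes any study suspensions or holds. The primary safety endpoint analyses will be based on a risk-benefit conclusion". No rate, threshold or comparison is given.

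Section 7.0 uses the same core definition and also includes suspensions and holds. It describes the problems further: "These problems potentially place subjects or others at greater risk of physical or psychological harm than was previously recognized". It then sets the scope of the reporting form in broader terms: "This form will be used to report any problem that is unforeseen or involves risk".

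Separately, 7.0 requires continuous adverse event assessment over the 24 weeks with CTCAE version 5.0 grading, and evaluates safety in anyone who received study treatment. The Appendix 4 log records, for each event, an SAE flag, the grade, whether treatment was held or withdrawn, and a five-level attribution: "Attribution Grading: A=unrelated B=unlikely C=possibly D=probably E=definitely".

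Sections 8.2 and 8.3 contain no adverse event endpoint. The nearest item is comfort-of-use in the device arm, in 8.3.

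**The concern.** The endpoint is a category made for prompt reporting to the IRB. Its test is whether a problem changes what is known about risk, not whether a participant was harmed. An event that is foreseen and occurs about as often and as severely as foreseen changes nothing in that sense, so a site following 8.1 has no reason to report it as an unanticipated problem.

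The trial's headline safety result, and the risk-benefit conclusion drawn from it, would then rest on a measure that can miss ordinary device harms. The graded and attributed data that would show them have no role in any stated endpoint. Two features make the count itself unsteady: the form-scope sentence in 7.0 is wider than the definition, and a study hold is added to the same tally as an event in one participant.

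**Working it through.** The protocol gives no safety rate, threshold or power, so there is no figure to reproduce. The check is a comparison of the texts, followed by an illustration with assumed rates.

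**Which events enter the endpoint?**

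| Event | Definition shared by 7.0 and 8.1 | Form-scope sentence in 7.0 |
|---|---|---|
| Device-related, at recognized frequency and severity | Need not count, since known risk is unchanged | Reportable if it is taken to involve risk |
| Device-related, more frequent or more severe than recognized | Can count, since risk exceeds what was known | Reportable |
| Unforeseen problem | Counts if it changes the risk | Reportable |
| Study suspension or hold | Counts, whatever the reason | Not mentioned in that sentence |

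The first row shows both the gap and the ambiguity. The definition leaves such events out, while the form-scope sentence may let them in. The endpoint is the occurrence of *reported* problems, so what sites choose to report determines the count. The fourth row shows the mixing of units: one hold concerns the whole study, one event concerns one participant.

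**Which endpoints use Appendix 4?** Section 8.1 (safety) uses unanticipated problems only. Sections 8.1 (effectiveness) and 8.2 use symptom scales, PGIC and the perceived-benefit form. Section 8.3 uses duration of response, time to benefit, comfort and perceived benefit. None uses grade, SAE flag, attribution or treatment held/withdrawn.

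**Illustration of size.**

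- Section 4.0 (Sample size): 100 to 200 participants randomized 1:1, so n = 100/2 = 50 to 200/2 = 100 on the device from the start.
- Assumed rate p of participants with a device-related adverse event within recognized risk: 2%, 5%, 10% or 20%.
- Expected number affected = n × p. Chance of at least one = 1 − (1 − p)^n.

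| Assumed p | Expected, n = 50 | Expected, n = 100 | P(at least one), n = 50 | P(at least one), n = 100 |
|---|---|---|---|---|
| 2% | 1 | 2 | 63.6% | 86.7% |
| 5% | 2.5 | 5 | 92.3% | 99.4% |
| 10% | 5 | 10 | 99.5% | >99.9% |
| 20% | 10 | 20 | >99.9% | >99.9% |

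Controls are offered crossover after week 12. If all accepted, 100 to 200 participants would be exposed and the expected numbers would double.

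**What an observed zero would show.** The exact one-sided 95% upper limit with no events is 1 − 0.05^(1/n). That is 1 − 0.05^(1/50) = 5.8% and 1 − 0.05^(1/100) = 3.0%. These limits apply to the proportion of participants with an unanticipated problem, not to the adverse event rate.

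**The case against.** The strongest reply has five parts.

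- **Adverse events are collected.** Section 7.0 sets the population, period and grading, and a statistical analysis plan that is not shown may well tabulate them. Nothing in 8.1 bars the risk-benefit judgement from using them. This stands as far as it goes: harm is recorded, and a missing table would be no finding. But the protocol itself fixes what the primary safety endpoint is, and a later table would not change that.
- **Foreseeable harm has a route in.** The form-scope sentence is broad, and the Appendix 3 form is laid out as an SAE report, with seriousness, grade and relationship to the device. This stands in part. Some foreseeable events, particularly serious ones, could be reported. It leaves open whether they count, which is why the claim is only that they need not enter.
- **The definition is already consistent.** This is correct. Sections 7.0 and 8.1 share the same core definition, and only the form-scope sentence in 7.0 differs.
- **Discomfort is analysed.** This is also correct: 8.3 covers comfort-of-use. It does not cover graded or attributed adverse events.
- **The choice is defensible.** The IRB's review placed the device in the nonsignificant-risk category. That supports keeping unanticipated problems in the endpoint, but not resting the endpoint on them alone.

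A reader might infer more than the text allows:

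- **Expected harms are ignored however frequent or severe.** Section 7.0 contradicts this, because risk beyond what was recognized can qualify.
- **The holds are merely administrative.** The protocol gives no reason for them, and they may be safety holds.
- **Zero unanticipated problems would count as meeting the endpoint.** Section 8.1 sets no pass mark.
- **Particular events, such as skin reaction or dizziness, are expected device effects.** The text shown contains no list of anticipated events, so this cannot be checked.

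**Conclusion.** The point holds in this form. The sole primary safety endpoint is reported unanticipated problems together with study suspensions and holds. Device-related adverse events at recognized frequency and severity need not enter it, and no endpoint in 8.1 to 8.3 uses the Appendix 4 safety fields. The endpoint can therefore read zero while device-attributed events have been recorded. Sites may also count the same event differently, because the 7.0 form-scope sentence is wider than the shared definition, and study-level and patient-level occurrences are mixed in one count.

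The size cannot be taken from the protocol. At an assumed 10% rate, 5 to 10 of 50 to 100 device participants would be affected without having to be counted; across assumed rates of 2% to 20% the range is 1 to 20. These figures assume that the events lie within recognized risk and that sites apply the narrower definition. The correction should be made, but it concerns how the endpoint is fixed and not a failure to record harm.

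**What to change.** 1. Add to the 8.1 safety endpoint the number and percentage of treated participants with at least one device-related adverse event, taken from Appendix 4. Show SAEs, CTCAE grade, and events leading to treatment being held or withdrawn. State in advance which attribution levels count as device-related and how exposure after crossover enters the denominator.
2. State in 8.1 that these data inform the risk-benefit conclusion.
3. Keep unanticipated problems but list them separately. List study suspensions or holds apart from them, each with its reason, so that a safety hold stays visible without being added to participant-level events.
4. Reconcile the form-scope sentence in 7.0 with the definition in 7.0 and 8.1, so that all sites count the same events.

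The cost is a wording change in two sections and one more table from data already collected. The reported safety figure will be less favourable than a count of unanticipated problems alone.
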